9.3.2 Safety Monitoring Committee (SMC)

PI's [name] and [name] will create a **Safety Monitoring Committee (SMC)**, which will meet at approximately six-month intervals via Skype or Zoom, as the committee is comprised of individuals in different locations. SMC members will represent expertise in psycho-oncology, in research monitoring and statistics. Members of the committee will agree to keep all information confidential. The committee members will review summaries of study progress to ensure that consent documentation is properly obtained and stored. They will review progress in subject recruitment and anticipated race/ethnicity participant representation. They will determine whether study coordinators and investigators are collecting and organizing data properly.

Data and Safety Monitoring

a. The SMC will monitor the study. The SMC is comprised of the following individuals:

[name] who has a background in epidemiology, statistics and public health and mental health research, she will monitor data collection and documentation as well as examine the data checks.

[name] who specializes in nursing research, and Psycho oncology and will oversee examining the fidelity checks and proper implementation of the intervention, subject recruitment and anticipated race/ethnicity participant representation.

Both PI's will be on the SMC

Co-I [name], who oversees the statistical analyses will also be part of the SMC. **PI [name]** will be responsible for submitting necessary reports to NINR.

- b. **Monitoring schedule for study safety:** The PI will review all events and unanticipated problems on a weekly basis. The SMC will monitor study safety bi-annually. Confidentiality: Study staff will notify the PI immediately of any breaches in participant confidentiality. The PI will notify SMC, IRB and NINR of breaches in confidentiality within 24 hours or notification by study staff.

Compliance of regulatory documents and study data accuracy and completeness will be maintained through an internal study team quality assurance process. Quality control will include semi-annual data verification and protocol compliance checks by the PI, Co-Is, and the Safety Monitoring Committee (SMC). Protocol adherence will be monitored by the PI and the SMC by auditing 5 cases semi-annually for compliance with IRB requirements, compliance with informed consent requirements, verification of source documents and compliance with the study protocol.

c. **Identification of AEs/unanticipated problems:**

Adverse event. For this study, since our subjects are breast cancer patients, they are likely to have many changes in their health status that are related to the time during treatment that they are participating in the study. Thus, since this is not a medical intervention study we will record only AEs that are possibly or definitely related to study participation. The following standard AE definitions are used:

Serious adverse event. An AE that results in any of the following:

- Death
- Life-threatening condition
- Inpatient hospitalization or prolongation of existing hospitalization
- Persistent or significant disability/incapacity

Not related. An AE for which a cause outside the study procedures is most plausible and/or a clinically plausible temporal sequence is inconsistent with the onset of the event.

Possibly related. An AE that follows a reasonable temporal sequence from the initiation of study procedures, but that could readily have been produced by a number of other factors.

Related. An AE that is clearly linked to the study procedures.

Review of AEs: The PI will compile quarterly report to the SMC detailing the study progress and participant status, any related or possibly related adverse events (AEs), and any protocol deviations. Unrelated or possibly related AEs will be reported to NINR in the yearly RPPR unless the event or unanticipated problem will affect the study risk level or progress, In this case, the PI will notify NINR staff within one week of completing the report.

Reporting of AEs: Serious Adverse Events will be reported immediately to the PI by study staff. The PI will report to SMC, IRB, NINR within 24 hours of notification by study staff. The PIs will follow OHRP Guidance on Reviewing and Reporting Unanticipated Problems Involving Risks to Subjects or Others and Adverse Events.

- d. **Multisite reporting:** PI [name] will report “unanticipated problems” involving risks to participants to the IRB, as well as NINR unrelated to the bi-annual reports of the monitoring committee that will submitted by the PIs. PI [name] will distribute the bi-annual and special (if unanticipated problems arise) reports to all site PIs for submission to their local IRBs. The SMC will also ensure compliance with the monitoring plan and reporting requirements across study sites. PI [name] will meet on a regular basis (every 3 months, at minimum) with all study staff to ensure compliance with the monitoring plan and reporting requirements across study sites. Furthermore, she will make sure the SMC is monitoring study progress as delineated above and submit reports as stated
- e. The PI's will conduct an ongoing assessment of external factors or relevant information (e.g., developments in the literature, results of related studies) that may have an impact on the safety of participants or on the ethics for the research study.
- f. The interim analysis will take place at the end of the first year of the study (after 6 months of data collection) and at the end of the second year (after 18 months of data collection). Since this is a mechanistic study, we are not concerned about not finding statistically significant differences between the groups, however, our pilot study findings do indicate that we should. In the case of unexpected findings, we will further explore the fidelity assessments to ensure the interventions are being conducted as designed (above and beyond the ongoing fidelity checks in place. PI [name] will closely monitor and supervise the research team at their respective sites, as well as conduct coordinated oversight of psychological status of all participating women taking part in the research. She will consult with PI [name] with any concern or consideration. PI [name] will also meet regularly with the research teams at the clinical sites and the University every other week to ensure appropriate conduct.

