7.3 Adverse Events and Serious Adverse Events

An **adverse event (AE)** is generally defined as any unfavorable and unintended diagnosis,

symptom, sign (including an abnormal laboratory finding), syndrome or disease which either occurs during the study, having been absent at baseline, or if present at baseline, appears to worsen. Adverse events are to be recording regardless of their relationship to the study intervention.

A **serious adverse event (SAE)** is generally defined as any untoward medical occurrence that results in death, is life threatening, requires inpatient hospitalization or prolongation of existing hospitalization, results in persistent or significant disability/incapacity, or is a congenital anomaly.

Adverse events are not expected because of the intervention or comparison groups.

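### Sections 7.3 and 9.3.2 contradict each other on whether unrelated adverse events are recorded, and 9.3.2 contradicts itself on reporting them

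*Protocol*

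**What the plan says.** Section 7.3 defines an AE broadly and then gives the recording rule: "Adverse events are to be recording regardless of their relationship to the study intervention". Section 7.2, where the handling of safety data would normally be set out, is marked not applicable.

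Section 9.3.2, item c, gives a different rule: "we will record only AEs that are possibly or definitely related to study participation". The reason offered is that these are breast cancer patients, so "they are likely to have many changes in their health status", and that the study does not test a medical intervention. The same item then defines three classes: not related, possibly related and related.

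Item c also covers reporting:

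- The principal investigator's (PI) quarterly report to the SMC covers "any related or possibly related adverse events (AEs), and any protocol deviations".
- For the funder: "Unrelated or possibly related AEs will be reported to NINR in the yearly RPPR". Events that affect the study's risk level or progress are to be notified sooner.
- For SAEs: "Serious Adverse Events will be reported immediately to the PI by study staff", and then "The PI will report to SMC, IRB, NINR within 24 hours of notification by study staff".

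The SAP does not mention adverse events.

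**The concern.** Two current sections give site staff opposite instructions for the same event, and neither says that it gives way to the other. Three hospitals could each settle the question differently, and AE counts would then not mean the same thing across sites.

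Under the 9.3.2 rule, a judgement about cause decides whether a non-serious event exists in the data at all. In a randomised trial, background illness should be similar in the two arms, so a comparison of all events by arm is informative without attributing each one. That comparison is lost for non-serious AEs judged unrelated. This matters because section 5.1 itself names distress from emotional content as a risk, and distress in a cancer patient is easily put down to the disease.

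**Working it through.** No arithmetic applies, and the plan states no figure to reproduce. The check sets the rules side by side for a **non-serious** AE, by the class it is given.

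| Class | Recorded under 7.3 | Recorded under 9.3.2 c | In quarterly SMC report | Named in yearly funder sentence |
|---|---|---|---|---|
| Not related | Yes | No | No | Yes |
| Possibly related | Yes | Yes | Yes | Yes |
| Related | Yes | Yes | Yes | No |

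1. **Between sections.** The rules agree for the lower two rows and are opposite for the first. The conflict is confined to events judged not related.
2. **Within 9.3.2.** The first row cannot be carried out: an event that is not recorded cannot be reported to the funder a year later. The last row is the reverse: a related, non-serious AE is recorded and goes to the SMC, but the funder sentence does not name it.
3. **Who judges.** No section assigns the relatedness decision or says whether the assessor is blinded. The definitions also overlap. The possibly-related class asks for plausible timing and allows other causes; the not-related class applies when an outside cause is the most plausible. Distress after a session, in a woman whose illness is the likelier cause, fits both. One choice records it and the other does not.
4. **Serious events.** The escalation sentences set no relatedness condition. However, item c defines an SAE as an AE with one of the listed outcomes, and that definition stands below the recording restriction. The restriction could therefore be read as reaching SAEs. This is an ambiguity, not a stated exclusion.

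**The case against.** The best defence is that 9.3.2 is the study-specific rule and 7.3 a generic definition, so 9.3.2 was meant to govern. Restricting AE recording for a group art intervention, for a stated reason, is a legitimate choice. This has some force. But nothing in the protocol gives 9.3.2 precedence, and the defence does not rescue 9.3.2's own funder sentence, which needs the unrelated events.

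Several stronger readings are tempting, and the documents do not support them.

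- *Events are filtered before anyone sees them.* Section 9.3.2 also says "The PI will review all events and unanticipated problems on a weekly basis". That could mean only recorded events, but the text does not say so.
- *Hospital admissions would never be counted.* An admission meets the SAE definition and goes to the SMC, ethics board and funder within 24 hours, with no relatedness test stated.
- *No comparison of harms between arms would be possible.* Depression, pain and fatigue are measured in both arms at baseline, after the intervention and at follow-up, whatever the cause (sections 6.2.2 and 6.2.4). The discontinuation text after section 7.5 refers to rises in mean depression. Worsening mood is therefore captured outside the AE record.
- *Unblinded therapists would do the filtering.* Table 4 lists therapists and PhD students as unblinded, but nothing gives them this task. What stands is that the assessor is unassigned.

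**Conclusion.** The contradiction between 7.3 and 9.3.2 is certain from the text, and so is the internal conflict in 9.3.2. As written, the rules cannot all be followed. The consequence is narrower: under the 9.3.2 rule, non-serious AEs judged unrelated are absent from the record and from the SMC's quarterly report, on a judgement with no named and blinded assessor.

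The size cannot be given as a number. The proportion of non-serious AEs lost equals the proportion judged not related, and the documents state neither that proportion nor any AE rate, so it could lie anywhere from none to nearly all. The conclusion rests on the wording alone and assumes that both sections are in force. It does not touch the efficacy or mediation analyses. It should be corrected, because the trial's AE counts cannot be interpreted until one rule applies.

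**What to change.** - **One rule.** Reconcile sections 7.3 and 9.3.2. The simplest course is to keep the 7.3 rule: record every AE in both arms, enter relatedness as a separate field, and tabulate AEs by arm.
- **If the restricted rule is kept for non-serious AEs,** state that all SAEs are recorded regardless of relatedness, and assign the relatedness judgement to existing site staff who are blinded to arm. Confirm that blinding first: sections 8.2 and 9.1 describe the research nurse as unblinded after randomisation, while section 8.3 and Table 4 say blinded.
- **Funder sentence.** Reword it so that related AEs are included and its scope matches the recording rule chosen.

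The cost is a wording change and one field on the AE form. Under the 7.3 rule there would be somewhat more AE entries, made at weekly contacts where the section 6.1 schedule already places AE assessment.

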9.3.3 Monitoring

PI [name] will closely monitor and supervise the research team at their respective sites, as well as conduct coordinated oversight of psychological status of all participating women taking part in the research. She will consult with PI [name] with any concern or consideration. PI [name] will also meet regularly with the research teams at the clinical sites and the University every other week to ensure appropriate conduct.

All local legal requirements regarding protection of personal data must be adhered to.

To ensure the quality and consistency of the intervention administration both the intervention and comparison groups in both Hebrew and Arabic will be scored against the treatment manual, using a check list which will be assessed daily by the research assistant who is blind to group allocation. Adherence to the study regimen will be defined as attending 80% of the group sessions, which will be monitored and recorded by the interventionist. Participant confidentiality will be well protected, as any data, specimens, forms, reports, and other records that leave the site will be identified only by a participant identification number (PID). All records will be kept in a locked file cabinet. All computer entry and networking programs will be done using Patient ID numbers only. Information will not be released without written permission of the participant, except as necessary for monitoring by IRB.

The Board will issue a report every six months to the PI and annually to the IRB.

9.3.4 Protocol Derivations

Should the PI identify discrepancies between the treatment manual and the fidelity scores PI [name] will immediately engage with the interventionist to discuss and provide guidance for getting back on track of the treatment protocol.

10. PARTICIPANT RIGHTS AND CONFIDENTIALITY

10.1 Institutional Review Board (IRB) Review

This protocol and the informed consent document and any subsequent modifications will be reviewed and approved by the IRB or ethics committee responsible for oversight

of the study. The consent form should be separate from the protocol document.

10.2 Informed Consent Forms

A signed consent form will be obtained from each participant. The consent form will describe the purpose of the study, the procedures to be followed, and the risks and benefits of participation. A copy will be given to each participant or legal guardian and this fact will be documented in the participant's record.

10.3 Participant Confidentiality

Any data, specimens, forms, reports, video recordings, and other records that leave the site will be identified only by a participant identification number (Participant ID, PID) to maintain confidentiality. All records will be kept in a locked file cabinet. All computer entry and networking programs will be done using PIDs only. Information will not be released without written permission of the participant, except as necessary for monitoring by IRB, the FDA, the NIH, and the OHRP.

11. SUPPLEMENTS/APPENDICES

I. Procedures Schedule Oct. 2018- Sept. 2021.

Table 3: Study Timeline						
Months	1-6	7-12	13-18	19-24	25-30	31-36
Prep/Training	X					
Team mtgs	X4	X4	X2	X1	X2	X6
Intervention		Cohort1	Cohort 2	Cohort 3	Cohort 4	
Data chk**		X		X		
Analysis				X (prelim)		X
Writing/discussion			X			X
Presentation at Conferences						X
Travel	[name] to Israel- Nov. 2018 [name] to Israel Jan 2019					Drs. [name], [name] and [name] to Tucson, AZ- spring/summer 2021
Final cohort begins mo. 25, allows final data mo. 31. **Data check/quality. Balance across arms on factors used in minimization technique will be monitored and adjusted.						

II. Informed Consent Form Template

DEMOGRAPHICS HEBREW-T0

דמוגרפי

אני עני על השאלות הבאות. בשאלות שיש לצד תשובה, אני הקيفי את התשובה המיטיבת לתראר את מצבך. בשאלות שאין לצד אפשרות תשובה, אני השלמי בעצמך:

גיל	ארץ לידה	ישראל	אחר	35-26	45-36	70-46	מעל 70
מצב משפחתי	האם יש לך ילדים?	רווקה	נשואה	גירושה	אלמנה	אחר:	אחר:
השכלה	האם את עבדת?	תיכוןית	לימודי תעודה	אקדמיית – תארים	אקדמיית – תואר ראשון	מתקדמיים	אחר
דת	האם את שולך?	יהודיה	מוסלמית	נוצריה	אחר	אחר	אחר
כיצד הייתה מגדרה את מידת הדתiot שלך?	האם את עוסקת באמנות?	דתיה	חילונית	מסורתית	אחר	כנים, בחוותני, מקצועני	כנים, בחוותני, מקצועני

DEMOGRAPHICS ARABIC T0

فيما يلي عدة أسئلة، يرجى احاطة رقم الإجابة الصحيحة وإكمال المعلومات الناقصة:

كم عمرك؟
 من فوق 70 70-46 45-36 35-26 25-18

1. ارض الولادة: اسرائيل اثيوبيا الاتحاد السوفيت ي سابقا آخر

2. الوضع العائلي: متوجزة ارمل/ة مطلقة مقصولة عازب/ة آخر

1. هل لديك اولاد؟ لا نعم

هل تسكن في: مدينة قرية مستوطنة آخر

1. ما هي درجتك التعليمية؟
 اخر اكاديمية - لقب ثالث اكاديمية - لقب ثالثي طالب/ة او لقب او اول

هل تعمل/ين؟
 الوضع الاقتصادي
 نعم لا اقل من الوسط اعلى من الوسط

الديانة
 يهودي/ة مسلم/ة مسيحي/ة درزي/ة آخر

كيف تعرف نفسك؟
 علماني/ة متدين/ة ارثوذوكسي/ة تقليدي/ة آخر

هل انخرطت في الفن؟
 لا نعم، بطريقة هواة نعم، مهنيا

PVQ-RR F Hebrew T0

המשפטים הבאים מטארים בקצרה אנשים שונים. קראי בבקשתו כל תיאור וחשי עד כמה האדם הזה דומה, או לא דומה לך. סמני X ביריבוע משMAL המתאר עד כמה האדם המתואר דומה לך.

עד כמה אדם זה דומה לך?

מאת דומה לי	דומה לי	די דומה לי	קצת דומה לי	לא דומה לי	בכל לא דומה לי	
	.1. חשוב לה לעצב את השקופותיה באופן עצמאי.					
	.2. חשוב לה שהמדינה שלה תהיה בטוחה ויציבה.					
	.3. חשוב לה לבנות בנעימים.					
	.4. חשוב לה להימנע מהרגיז אנשים אחרים.					
	.5. חשוב לה שהחברים והפיגועים בחברה יהיו מוגנים.					
	.6. חשוב לה שאנשים יעשו מה שהוא אומרת שעיליהם לעשות.					
	.7. חשוב לה לא לראות את עצמה ראהיה ליותר מזרים.					
	.8. חשוב לה לשמר על הטבע.					
	.9. חשוב לה שאף אחד אף פעם לא יביסש אותה.					
	.10. חשוב לה לחפש כל הזמן דברים שונים לעשות.					
	.11. חשוב לה לדאוג לאנשים הקרובים אליה.					
	.12. חשוב לה שיהיה לה הכוח שיכסיף יכול להביא אותנו.					
	.13. חשוב לה מאוד להימנע ממחלות ולשמור על בריאותה.					
	.14. חשוב לה להיות סובלני כלפי כל סוגי האנשים והקבוצות.					
	.15. חשוב לה לעולם לא להפר חוקים או תקנות.					
	.16. חשוב לה לקבל בעצמה את החלטות שלה לגבי חייו.					
	.17. חשוב לה שיהיו לה שאיפות בחיים.					
	.18. חשוב לה לשמר ערכים ודרך חשיבה מסורתית.					
	.19. חשוב לה שאנשים שהיא מכירה יתנו בה אמון מלא.					
	.20. חשוב לה להיות עשיר.					
	.21. חשוב לה להשתתף בפעולות להגנה על הטבע.					
	.22. חשוב לה לא לעצבן אף אחד אף פעם.					
	.23. חשוב לה לפתח דעתות משלה.					

עד כמה אדם זה דומה לך?

| לא דומה לך | בכל לא דומה לך | |
|--------------------------|--------------------------|--------------------------|--------------------------|--------------------------|--------------------------|--|
|  | 24. חשוב לך להגן על התדמית שלה בעיני אחרים. |
|  | 25. מאמין חשוב לך לעזור לאנשים היקרים לך. |
|  | 26. חשוב לך להיות בטוחה ומוגנת באופן אישי. |
|  | 27. חשוב לך להיות חברותה אמינה שנית לבטוח בו. |
|  | 28. חשוב לך לנקוט סיוכנים שהופכים את החיים למרגשים. |
|  | 29. חשוב לך שיחיה לה כוחה לגרום לאנשים לעשות מה שהיא רוצה. |
|  | 30. חשוב לך לתכנן את הפעולות שלה באופן עצמאי. |
|  | 31. חשוב לך לנוהג לפי החוקים גם כשאף אחד לא מסתכל. |
|  | 32. חשוב לך להצליח מואוד בחיים. |
|  | 33. חשוב לך לדבוק במנגנים משפחתיים או במנגנים דתניים. |
|  | 34. חשוב לך להקשיב לאנשים השונים ממנה ולהבין אותם. |
|  | 35. חשוב לך שמדינה תהיה חזקה ומסוגלת להגן על אזרחיה. |
|  | 36. חשוב לך ליהנות מתענוגות החיים. |
|  | 37. חשוב לך שלכל אדם בעולם יהיו הזדמנויות שותפות בחיים. |
|  | 38. חשוב לך להיות ענוה. |
|  | 39. חשוב לך לפענה ולהבין דברים בעצמה. |
|  | 40. חשוב לך לכבד את המנהיגים המסורתיים של התרבות שלך. |
|  | 41. חשוב לך להיות זאת שאומרת לאחרים מה לעשות. |
|  | 42. חשוב לך לצית לכל החוקים. |
|  | 43. חשוב לך שיחיו לה כל מיני חוויות חדשות. |
|  | 44. חשוב לך שיחיו לה דברים יקרים המעידים על עושרה. |
|  | 45. חשוב לך להגן על הטבע מהרס ומזיהום. |
|  | 46. חשוב לך לנצל כל הזדמנויות ליהנות. |
|  | 47. חשוב לך לדאוג לכל צורך של יקירה. |
|  | 48. חשוב לך שאנשים יכירו בהישגים שלה. |
|  | 49. חשוב לך לעולם לא להיות מושפלה. |

עד כמה אדם זה דומה לך?

מאנ' דומה לי	דומה לי	די דומה	קצת דומה	לא דומה לי	בכל לא דומה לי	
	50. חשוב לה שמדינה תגן על עצמה מפני כל איום.					
	51. חשוב לה אף פעם לא להכweis אנשים אחרים.					
	52. חשוב לה שוכלים יקבלו יחס צודק, גם אנשים שאיינה מכירה.					
	53. חשוב לה להימנע מכל דבר מסוכן.					
	54. חשוב לה להסתפק במה שיש לה ולא לבקש יותר.					
	55. חשוב לה שכל חבריה ובני משפחתה יוכלו לסייע עליה לחלווטין.					
	56. חשוב לה להיות חופשית להחלטת עצמה מה היא עושה.					
	57. חשוב לה לקבל אנשים אחרים גם כשיינה מסכימה איתם.					

PVQ-RR F ARABIC T0

٦٣٦١

استبيان القيم الوصفية - النسخة العربية (PVQ-RR)، إناث (2013/10)

فيما يلي نقدم وصفاً مختصراً لأشخاص مختلفين. الرجاء قراءة كل وصف والتفكير في مدى التشابه أو الاختلاف بينك وبين الشخص الموصوف. ثم نرجو وضع إشارة X في المربع الذي يشير إلى مدى التشابه بينك وبين الشخص الموصوف.

إلى أي مدى تشبهك هذه الشخصية؟

تشبهني كثيراً	تشبهني حد ما	تشبهني قليلًا	لا تشبهني قليلًا	لا تشبهني أبداً	1. من المهم لها تكون آرائها بشكل مستقل.
	2. من المهم لها أن يكون وطنها آمناً ومستقراً.				
	3. من المهم لها قضاء أوقات ممتعة.				
	4. من المهم لها أن تتجنب مضايقة الآخرين.				
	5. من المهم لها أن تتم حماية الضعفاء والمساكين والمهمشين في المجتمع.				
	6. من المهم لها أن يفعل الآخرون ما تأمرهم بفعله.				
	7. من المهم لها أن لا تعتقد أبداً أنها تستحق أكثر من الآخرين.				
	8. من المهم لها المساهمة في حماية الطبيعة.				
	9. من المهم لها أن لا تتعرض أبداً لتشويه السمعة من قبل أي شخص.				
	10. من المهم لها البحث دائمًا عن أشياء مختلفة لقيامها.				
	11. من المهم لها الاهتمام بالأشخاص المقربين إليها.				
	12. من المهم لها امتلاك القوة التي يمكن للمال أن يوفرها.				
	13. من المهم جدًا لها أن تتجنب الأمراض وأن تحافظ على صحتها.				
	14. من المهم لها تقبلاً كافياً لностей نواعي الناس والمجتمعات السكانية.				
	15. من المهم لها أن لا تخالف أبداً القوانين والنظم.				
	16. من المهم لها أن تتخذ قراراتها بنفسها بخصوص حياتها.				
	17. من المهم لها أن تكون طموحة في حياتها.				
	18. من المهم لها الحفاظ على طرق التفكير والقيم المجتمعية التقليدية/المُحافظة.				
	19. من المهم لها أن يثق بها الأشخاص الذين تعرفهم بصورة كاملة.				

كثيرا	تشبهني	تشبهني الى تشبهني	تشبهني الى حد ما	تشبهني قليلًا	لا تشبهني قليلًا	لا تشبهني	أبدا	20. من المهم لها أن تكون غنيةً.
	21. من المهم لها المشاركة بالفعاليات التي تهدف لحماية الطبيعة.							
	22. من المهم لها الـأثر عـاجـداـ.							
	23. من المهم لها تطوير آرائـهاـ الشـخصـيةـ.							
	24. من المهم لها الدافعـعنـ سـمعـتهاـأـمـامـ النـاسـ.							
	25. من المهم جــداـ لها أن تــسـاعـدـ الاـشـخـاصـ الأـعـزـاءـ بــالـنـسـبـةـ لــهـاـ.							
	26. من المهم لهاـنـ تــعـيـشـ بــأـمـنـ وــأـمـانـ.							
	27. من المهم لهاـنـ تكونـ صـدـيقـةـ وــفـيـةـ وــيـمـكـنـ الــاعـتـمـادـ عــلـيـهـاـ.							
	28. من المهم لهاـنـ الــقـيـامـ بــالـمـخـاطـرـ الــتـيـ تــجـعـلـ الــحـيـاةـ مــشـوـقـةـ.							
	29. من المهم لهاـنـ اـمـتـالـ الــقـوـةـ الــتـيـ تــمـكـنـهاـ مــنـ إـمـلـاءـ إـرـادـتـهاـ عــلـىـ الــأـخـرـينـ.							
	30. من المهم لهاـنـ التــخـطـيـطـ لــنـشـاطـاتـهاـ بــاسـتـقـالـيـةـ.							
	31. من المهم لهاـنـ الــانـصـيـاعـ لــلـقـوـانـينـ حــتـىـ إـنـ يــكـنـ أـحـدـ يــرـاقـهاـ.							
	32. من المهم لهاـنـ تكونـ نـاجـحةـ جــداـ.							
	33. من المهم لهاـنـ تــتـبـعـ عــادـاتـ عــائـلـتـهاـ أوــقـالـيـدـ دــينـهاـ.							
	34. من المهم لهاـنـ الــاسـتـمـاعـ إـلـىـ الــاـشـخـاصـ الــمـخـتـلـفـينـ عــنـهـاـ وــفـهـمـهـمـ.							
	35. من المهم لهاـنـ تكونـ الــوـلـةـ قــوـيـةـ وــقــادـرـةـ عــلـىـ الدــافـعـ عــنـ مــوـاـطـنـيـهـاـ.							
	36. من المهم لهاـنـ التــمـنـعـ بــمـلـذـاتـ الــحـيـاةـ.							
	37. من المهم لهاـنـ تــتـوـفـرـ فــرـصـ مــتـسـاوـيـلـكـلـ شــخـصـ فــيـ الــعــالـمـ.							
	38. من المهم لهاـنـ تكونـ مــتـواـضـعـةـ وــزــاهـدـةـ.							
	39. من المهم لهاـنـ أـنـ ثــدـرـ كــالـشـيـاءـ بــنـفـسـهـاـ.							
	40. من المهم لهاـنـ اـحـتـرـامـ العــادـاتـ وــالـقــالـيـدـ الــخــاصـةـ بــمــجــمــعــهــاـ.							
	41. من المهم لهاـنـ أـنـ تــكـوـنـ هــيـ الشــخــصـ الــذـيـخــرـ الــأـخــرـينـ بــمــاـ عــلـيـهـ فــعــلـهـ.							
	42. من المهم لهاـنـ تــطـيـعـ كــافــةـ الــقــوـانــينـ.							
	43. من المهم لهاـنـ تــعـيـشـ تــجـارـبـ جــدـيـدةـ بــكــافــةـ اـشــكــالــهــاـ.							
	44. من المهم لهاـنـ تــمـتـلـكـ أـشــيـاءـ ثــمـيـنـةـ تــظـهـرـ مــدـىـ ثــرـائـهـاـ.							

تشبهني كثيرا	تشبهني الى حد ما	تشبهني قليلا	لا تشبهني قليلًا	لا تشبهني أبداً	45. من المهم لها أن تتم حماية البيئة الطبيعية من التدمير أو التلوث.
	46. من المهم لها أن تستغل كل فرصة لثمضي وقتاً في الاستماع.				
	47. من المهم لها أن تعتني بكلفة احتياجات الأشخاص الأعزاء على قلبها.				
	48. من المهم لها أن يلاحظ الآخرون إنجازاتها.				
	49. من المهم لها أن لا تتعرض للإهانة أبداً.				
	50. من المهم لها أن تحمي دولتها نفسها من كافة التهديدات.				
	51. من المهم لها أن لا تُغضِّب الآخرين أبداً.				
	52. من المهم لها أن يحظى كل إنسان - حتى الذين لا يُعرفُون - بمعاملة عادلة.				
	53. من المهم لها أن تجتنب أي شيء قد يعرضها للخطر.				
	54. من المهم لها أن تكون قنوعَهُما تمالك وأن لا تطلب المزيد.				
